### **3.2 DISCUSSION OF TRIAL DESIGN, INCLUDING THE CHOICE OF CONTROL GROUP**

For single-rising dose trials, the sequential rising dose design described in Section [3.1](#) is viewed favourably under the provision not to expose the subjects involved to undue risks.

Single-blind conditions regarding the subject's treatment (active or placebo) are maintained within each dose group. However, subjects and investigators will be aware of the dose of drug administered. The disadvantage of the trial design is a possible observer bias with regard to the dose-dependent effects; in addition, the sequential dosing of groups could potentially result in time-related effects. However, as such effects are expected to be small relative to the differences between the doses in the broad range investigated, unbiased comparisons between treatments can still be expected.

It is standard in single or multiple rising dose trials involving healthy volunteers to include a placebo group to control for safety and tolerability of the trial medication. Each dose group consists of 8 subjects, with 6 on active treatment, and 2 on placebo. For data analysis purposes, the placebo control group will include all subjects of all dose groups treated with placebo. Six subjects per active treatment group are generally considered to be sufficient for the exploratory evaluation of pharmacokinetics.

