### 7.3 PLANNED ANALYSES

#### Analysis sets

Statistical analyses will be based on the following analysis sets:

- Treated set (TS): The treated set includes all subjects who were randomized and treated with at least one dose of study drug. The treatment assignment will be determined based on the first treatment the subjects received. The treated set will be used for safety analyses.
- Pharmacokinetic parameter analysis set (PKS): This set includes all subjects in the treated set (TS) who provide at least one PK endpoint that was not excluded due to a protocol violation relevant to the evaluation of PK or due to PK non-evaluability (as specified in the following subsection 'Pharmacokinetics'). Thus, a subject will be included in the PKS, even if he/she contributes only one PK parameter value for one period to the statistical assessment. Descriptive and model based analyses of PK parameters will be based on the PKS.
- ECG pharmacokinetic concentration set (ECGPCS): This subject set includes all subjects from the TS who provide at least one pair of a valid drug plasma concentration and a corresponding (i.e. time-matched) ECG endpoint to be used in the exposure-response analyses. For placebo subjects, the plasma concentration is set to zero and hence always considered as valid. The decision whether a time deviation between PK blood sampling and ECG recording is acceptable (and thus whether the pair of values will be used) is to be made no later than at the Report Planning Meeting before data base lock. The ECGPCS will be used for the exposure-response analyses.

Proprietary confidential information © 2021 Boehringer Ingelheim International GmbH or one or more of its affiliated companies

Adherence to the protocol will be assessed by the trial team. Important protocol violation (IPV) categories will be specified in the TSAP, IPVs will be identified no later than in the Report Planning Meeting, and the IPV categories will be updated as needed.

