### 7.3.4 Safety analyses

Safety will be assessed as defined by the endpoints listed in Section [2.1.2](#) and [2.2.2](#) based on the treated set (TS). Safety analyses will be descriptive in nature and will be based on BI standards.

Proprietary confidential information © 2021 Boehringer Ingelheim International GmbH or one or more of its affiliated companies

For all analyses the treatment actually administered (= treatment at onset) to the subject will be used (any deviations from the randomised treatment will be discussed in the minutes of the Report Planning Meeting).

Treatments will be compared in a descriptive way. The placebo group in the safety evaluation will consist of all subjects treated with placebo, regardless of the dose group in which they were treated. The test treatment groups will be compared to the placebo group in a descriptive way. Tabulations of frequencies/proportions will be used for the evaluation of categorical (qualitative) data, and tabulations of descriptive statistics will be used to analyse continuous (quantitative) data.

Measurements (such as ECGs, vital signs, or laboratory parameters) or AEs will be assigned to treatments (see Section [4.1](#)) based on the actual treatment at the planned time of the measurement or on the recorded time of AE onset (concept of treatment-emergent AEs).

Therefore, measurements planned or AEs recorded prior to intake of trial medication will be assigned to the screening period, those between the trial medication intake and end of REP (see Section [1.2.6](#)) will be assigned to the treatment period. Events occurring after the REP but prior to trial termination date will be assigned to 'follow-up'. These assignments including the corresponding time intervals will be defined in detail in the TSAP. Note that AEs occurring after the last per protocol contact but entered before database lock will be reported to Pharmacovigilance only and will not be captured in the trial database.

Additionally, further treatment intervals (called analysing treatments) may be defined in the TSAP in order to provide summary statistics for other than above periods, such as combined treatments, on-treatment totals, or periods without treatment effects (such as screening and post-study intervals).

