## **7.6 RANDOMISATION**

Each dose group will be divided into three cohorts. The subjects of the first 2 cohorts (2 subjects per cohort) will not be randomized to maintain a treatment sequence of active-placebo (Cohort 1) and active-active (Cohort 2) due to safety reasons. In the third cohort of each dose level (4 subjects) the subjects will be assigned to active or placebo treatment using a 3:1 allocation ratio (test treatment to placebo).

The sponsor will arrange for the randomisation as well as packaging and labelling of trial medication. The randomisation list will be generated using a validated system that uses a pseudo-random number generator and a supplied seed number so that the resulting allocation is both reproducible and non-predictable.

The randomisation list will contain additional blocks to allow for subject replacement (refer to Section [3.3.5](#)).

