## **7.7 DETERMINATION OF SAMPLE SIZE**

It is planned to include a total of 64 subjects in this trial. The planned sample size is not based on a power calculation. The size of 8 subjects per dose group (6 on active treatment, and 2 on placebo) is commonly used in single-rising dose studies of the present type and is in general considered as sufficient for the exploratory evaluation of single dose safety and pharmacokinetics.

Additional subjects may be entered to allow testing of additional doses on the basis of experience gained during the trial conduct (e.g. preliminary PK data), provided the planned and approved highest dose will not be exceeded. Thus, the actual number of subjects entered may exceed 64, but will not exceed 72 subjects entered.

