Consistency check listings (for identification of deviations of time windows) and a list of protocol deviations (e.g. deviations in drug administration, in blood sampling times, etc.) will be provided to be discussed at the Report Planning Meeting (RPM). At this meeting, all manual deviations identified at the sites by the CRAs and deviations too complex to program will be reviewed by the trial team to decide which are considered important. For definition of important protocol deviations (iPD), and for the process of identification of these, refer to the Boehringer Ingelheim (BI) SOP "Identify and Manage Important Protocol Deviations (iPD)" ([2](#)).

Handling of iPDs in analysis is included in the DV domain specifications and stored within the TMF in EDMS.

If any iPDs are identified, they are to be summarised into categories and will be captured in the decision log ([3](#)).

Protocol deviations will be summarised and listed.

6.3 **SUBJECT SETS ANALYSED**

- Treated set (TS):

The treated set includes all subjects who were randomised and treated with at least one

dose of study drug. The treatment assignment will be determined based on the first treatment the subjects received.

This is the full analysis set population in the sense of ICH-E9 (1). It is used for safety analysis. The ECG analyses are performed on the TS, except for the exposure-response analyses, which are performed on the ECGPCS defined below.

- PK parameter analysis set (PKS):

This set includes all subjects in the treated set (TS) who provide at least one PK endpoint that was not excluded due to a protocol deviation relevant to the evaluation of PK or due to PK non-evaluability. Thus, a subject will be included in the PKS, even if he contributes only one PK parameter value for one period to the statistical assessment.

Descriptive and model based analyses of PK parameters will be based on the PKS.

The descriptive analysis of PK concentrations will be based on the ADS ADPC as described at the beginning of [Section 7](#).

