7. PLANNED ANALYSIS

The placebo group in the safety evaluation will consist of all placebo treated subjects, regardless of the dose group in which they were treated.

Safety analysis (refer to [Section 7.8](#)) will be performed by [REDACTED] and will be presented in Sections 15.1 to 15.4 of the CTR and in Appendix 16.2 and 16.1.13.1.

Inferential statistical analyses of PK endpoints (refer to [Section 7.5.2](#)) will also be performed by [REDACTED] and will be presented in Section 15.5 of the CTR and in Appendix 16.1.13.3.

Descriptive data analysis of PK parameters and concentrations will be performed by the department of [REDACTED] at [REDACTED] and will be presented in Section 15.6 of the CTR.

Descriptive data analysis of PD parameters and concentrations will be performed by the department of [REDACTED] at [REDACTED] and will be presented in Section 15.7 of the CTR.

The format of the listings and tables will follow the standards defined in the BI corporate guideline “Reporting of Clinical Trials and Project Summaries” [001-MCG-159] ([6](#)) with the exception of those generated for PK and PD calculations.

The individual values of all subjects will be listed, sorted by treatment group, subject number, and visit. The listings will be included in Appendix 16.2 of the CTR.

For end-of-text tables, the set of summary statistics for non-PK parameters is:

N	number of non-missing observations
Mean	arithmetic mean
SD	standard deviation
Min	minimum
Median	median
Max	maximum

For analyte concentrations, the following descriptive statistics will additionally be calculated:

CV	arithmetic coefficient of variation
gMean	geometric mean
gCV	geometric coefficient of variation

For PK parameters, the following descriptive statistics will additionally be calculated:

CV	arithmetic coefficient of variation
gMean	geometric mean
gCV	geometric coefficient of variation
P10	10th percentile

Q1	1st quartile
Q3	3rd quartile
P90	90th percentile

The data format for descriptive statistics of concentrations will be identical with the data format of the respective concentrations. The descriptive statistics of PK parameters will be calculated using the individual values with the number of decimal places as provided by the evaluation program. Then the individual values as well as the descriptive statistics will be reported with three significant digits in the CTR.

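### The treated set requires randomisation, but half of the planned subjects are assigned in fixed order and are not randomised

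*Protocol*

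**What the plan says.** Protocol 7.3 (Analysis sets) states: "The treated set includes all subjects who were randomized and treated with at least one dose of study drug". SAP 6.3 uses the same condition, "The treated set includes all subjects who were randomised and treated with at least one" dose of study drug, and calls this the full analysis set in the ICH E9 sense. The treated set (TS) carries the primary endpoint (Protocol 7.3.1) and all safety analyses (Protocol 7.3.4, SAP 7.8). Both documents define the PK parameter set (PKS) and the ECG concentration set (ECGPCS) as subsets of the TS.

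Protocol 7.6 says of the fixed-order cohorts: "The subjects of the first 2 cohorts (2 subjects per cohort) will not be randomized". Protocol 3.1 labels Cohorts 1 and 2 as fixed order and only Cohort 3 as randomised, and Protocol 4.1.3 makes the same distinction.

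On who is to be analysed, Protocol 3.2 says: "For data analysis purposes, the placebo control group will include all subjects of all dose groups treated with placebo". Protocol 7.3.4 agrees ("The placebo group in the safety evaluation will consist of all subjects treated with placebo"), as does SAP 7 ("The placebo group in the safety evaluation will consist of all placebo treated subjects"). On the active arms, Protocol 3.2 says: "Six subjects per active treatment group are generally considered to be sufficient for the exploratory evaluation of pharmacokinetics". Protocol 7.7 adds: "The size of 8 subjects per dose group (6 on active treatment, and 2 on placebo) is commonly used".

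**The concern.** The documents give *randomised* a specific meaning that excludes four of the eight subjects in each dose group, then make randomisation a condition of entry to the TS. No section extends the term to subjects assigned in fixed order. The set definition and the placebo-group rule therefore cannot both be followed. A programmer who selects on randomisation status gets one denominator for the percentage of subjects with drug-related adverse events, and a programmer who follows the placebo-pooling statement gets another.

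Because the PKS and ECGPCS are nested in the TS, the same word also governs AUC0-∞ and Cmax, the dose-proportionality model and the concentration-QTcF model. The point does not extend to the descriptive concentration summaries, which SAP 6.3 bases on a separate analysis data set, or to the redacted column in SAP Table 6.3: 1.

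**Working it through.** **Reproducing the planned numbers** (cohort composition from Protocol 3.1)

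| Cohort | Assignment | Active | Placebo |
|---|---|---|---|
| 1 | fixed order | 1 | 1 |
| 2 | fixed order | 2 | 0 |
| 3 | randomised | 3 | 1 |
| Dose group | | 6 | 2 |

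Eight dose groups give 8 × 8 = 64 subjects, 8 × 6 = 48 active and 8 × 2 = 16 placebo. The 64 matches Protocol 7.7. Seven groups give 42 active and 14 placebo, matching the subjects already dosed according to Protocol 1.2.5.

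**Applying the TS definition literally** (Cohort 3 only)

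| | Intended | Literal |
|---|---|---|
| Active per dose | 6 | 3 |
| Active, 8 groups | 48 | 8 × 3 = 24 |
| Placebo, 8 groups | 16 | 8 × 1 = 8 |
| Total, 8 groups | 64 | 32 |
| Total, 7 completed groups | 56 (42 + 14) | 28 (21 + 7) |

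**What the literal set would do to the primary endpoint.** The chance of seeing at least one affected subject at a dose is 1 − (1 − p)^n. The documents give no event rate, so p is assumed.

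- p = 10%: 1 − 0.9^6 = 0.47 against 1 − 0.9^3 = 0.27.
- p = 20%: 1 − 0.8^6 = 0.74 against 1 − 0.8^3 = 0.49.

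**What it would do to the power model.** The 90% half-width for the slope is t(0.95, N − 2) × σ / √(m × S). Here m is the number of active subjects per dose, N = 8m, and S is the sum of squares of ln(dose) about its mean. For 1, 3, 6, 12, 25, 50, 90 and 160 mg, S = 21.316.

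- m = 6, N = 48: t = 1.679, so 1.679σ/√127.9 = 0.1484σ.
- m = 3, N = 24: t = 1.717, so 1.717σ/√63.95 = 0.2147σ.
- Ratio: 0.2147/0.1484 = 1.45.

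With σ = √ln(1 + gCV²) and assumed between-subject gCVs:

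| Assumed gCV | σ | Half-width, m = 6 | Half-width, m = 3 |
|---|---|---|---|
| 20% | 0.198 | 0.029 | 0.043 |
| 30% | 0.294 | 0.044 | 0.063 |
| 50% | 0.472 | 0.070 | 0.101 |

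All of these describe the literal reading. They do not predict what the report will contain.

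**The case against.** The best defence is that the intent is obvious and the wording is probably template text.

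- The set is called the treated set. SAP 6.2 looks for deviations in all treated subjects, and SAP 7 lists individual values for all subjects. Protocol 3.3.4 reports the data of anyone withdrawn after dosing.
- The documents also use *randomised* loosely. Protocol 4.1.3 assigns subjects from the randomisation list without naming a cohort in that sentence. Protocol 7.3.4 speaks of the randomised treatment for all analyses. SAP 8 equates the end of enrolment with the end of randomisation.
- The implementing specification cited in SAP 6.1 is not available, so how fixed-order subjects are coded is unknown.
- The statements about six active subjects per dose justify the design and are not analysis-set rules.
- The study tests no hypotheses.

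Much of this stands. It establishes the intent and makes actual loss of data unlikely. The conflict in the active arms is an inference, whereas the placebo conflict is explicit. But loose usage elsewhere does not define the term and cannot override the plain statement in Protocol 7.6. The list in Protocol 4.1.3 is introduced for random assignment, directly after that has been confined to Cohort 3. A SAP is meant to state the selection rule exactly, and here the rule contradicts its own placebo group.

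**Conclusion.** The concern holds. As written, the TS contains 32 of 64 planned subjects, and the placebo group defined elsewhere in the same documents (16) cannot be drawn from it (8). The head counts follow directly from the cohort structure and need no assumption beyond full enrolment. The event probabilities and half-widths depend on the assumed rates and gCVs, and apply only if the definition is followed to the letter. If the evident intent is followed, the effect on every result is zero.

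This is an error in a stated rule for the primary-endpoint population. It casts no doubt on the design or the sample size. SAP Section 4 is accurate in declaring no change from the protocol, but that also means the error was carried forward uncorrected. It should be fixed.

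**What to change.** In SAP 6.3, delete the two words *randomised and*, so that the TS comprises every subject treated with at least one dose of study drug. Add no wording about cohorts: the simpler definition also covers replacement subjects, who take the treatment of the subject they replace (Protocol 3.3.5). The PKS and ECGPCS definitions then need no edit.

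Record the correction in one line in SAP Section 4. Make the matching deletion in Protocol 7.3 when the protocol is next amended; this point alone does not justify a separate amendment. There is no operational cost and no change to sample size, procedures or data collection.

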#### Pharmacokinetics

The pharmacokinetic parameters listed in Section 2.1.3 and Section 2.2.2.2 for drug BI 1595043 will be calculated by means of non-compartmental analysis. Non-compartmental PK parameters will be calculated based on actual sampling times using a validated pharmacokinetic software (██████████). Descriptive statistics will be used to evaluate plasma concentration data and PK parameters. The derivation of PK parameters will be according to the relevant SOP of the Sponsor ([001-MCS-36-472](#)).

Plasma ████████ concentration data and parameters of a subject will be included in the statistical pharmacokinetic (PK) analyses if they are not flagged for exclusion due to a protocol violation relevant to the evaluation of PK (to be decided no later than in the Report Planning Meeting) or due to PK non-evaluability (as revealed during data analysis, based on the criteria specified below). Exclusion of a subject's data will be documented in the CTR.

Relevant protocol violations may be

- Incorrect trial medication taken, i.e. the subject received at least one dose of trial medication the subject was not assigned to
- Incorrect dose of trial medication taken
- Use of restricted medications

Plasma ████████ concentrations and/or parameters of a subject will be considered as non-evaluable, if for example

- The subject experienced emesis that occurred at or before two times median  $t_{max}$  of the respective treatment (Median  $t_{max}$  is to be determined excluding the subjects experiencing emesis),
- Missing samples/concentration data at important phases of PK disposition curve.

Plasma ████████ concentration data and parameters of a subject which is flagged for exclusion will be reported with its individual values but will not be included in the statistical analyses.

Only concentration values within the validated concentration range and actual sampling times will be used for the calculation of pharmacokinetic parameters. Concentrations used in the pharmacokinetic calculations will be in the same format as in the bioanalytical report (that is to the same number of decimal places provided in the bioanalytical report).

Proprietary confidential information © 2021 Boehringer Ingelheim International GmbH or one or more of its affiliated companies

If a pre-dose concentration value is greater than 5% of  $C_{max}$ , the subject's pharmacokinetic data will be not included in any statistical evaluations, in accordance with international guidances. The individual pharmacokinetic parameters of such a subject will be calculated and listed separately. If a pre-dose concentration is above BLQ, but less than or equal to 5% of the subject's  $C_{max}$  value, the subject's data without any adjustments will be included in all pharmacokinetic measurements and calculations.

Every effort will be made to include all concentration data in an analysis. If not possible, a case to case decision is required whether the value should only be excluded from half-life estimation or the complete analysis.

- If a concentration is only excluded from half-life determination, it will be used for all other calculations (e.g. descriptive statistics) and for graphical presentation.
- If a concentration value is excluded from all calculations, it will not be presented graphically or used for the calculation of descriptive statistics and parameter determination. However the excluded concentration itself will be listed in the clinical trial report associated with an appropriate flag.

Descriptive statistics of parameters are calculated only when at least 2/3 of the individual parameter estimates of a certain parameter are available. If the actual sampling time will not be recorded or will be missing for a certain time point, the planned time will generally be used for this time point instead. Pharmacokinetic parameters which cannot be determined will be identified by "not calculated" (NC).

### **7.3.1 Primary endpoint analyses**

The primary endpoint as specified in Section [2.1.2](#) will be derived according to BI standards. The analysis will be based on the treated set (TS) and will be descriptive in nature. See Section [7.3.4](#) for further details.

### **7.3.2 Secondary endpoint analyses**

#### Primary analyses

The secondary endpoints (refer to Section [2.1.3](#)) will be analysed descriptively. Analyses will be performed for the parent drug and for metabolites.

### Further exploratory analyses

Dose proportionality will be explored via graphical checks and, if applicable, via the power model stated below. The analysis will be performed for the pharmacokinetic endpoints  $AUC_{0-\infty}$  and  $C_{max}$  specified in Section [2.1.3](#).

The power model describes the functional relationship between the dose level and PK endpoint on the log scale via

[figure not shown]
$$y_{km} = \log(x_{km}) = \mu + \beta \cdot \log(D_k) + e_{km},$$

where

$y_{km}$  logarithm of response (PK parameter) measured on subject m receiving dose k,  
 $x_{km}$  response (PK parameter) measured on subject m receiving dose k,  
 $\mu$  the overall mean,  
 $\beta$  slope parameter of linear regression line,  
 $D_k$  level of dose k,  $k=1,\dots,8$ ,  
 $e_{km}$  the random error associated with the  $m^{th}$  subject who was administered dose k  
( $e_{km} \sim N(0, \sigma^2)$  iid).

The slope parameter  $\beta$  together with its two-sided 90% confidence interval will be estimated. Additionally, the r-fold change  $r^{\beta-1}$  together with its 90% CI will be derived.

As some small doses at the beginning and/or some doses at the upper end might not contribute to the linear relationship between dose and PK, dose proportionality over the entire dose range investigated might not be shown. In that case an attempt will be made to identify a subrange of at least 3 consecutive doses where dose proportionality can be concluded.

